### 12.2. Definitions

#### 12.2.1. Adverse Event

An *adverse event* is any untoward medical event associated with the use of a drug in humans, whether or not considered drug related. An adverse event can therefore be any unfavorable and unintended sign (including an abnormal laboratory finding, for example), symptom, or disease temporally associated with the use of a drug and does not imply any judgment about causality.

An untoward medical event which occurs outside the period of follow-up as defined in the protocol will not be considered an adverse event. Worsening of a medical condition for which the efficacy of the study drug is being evaluated will not be considered an adverse event.

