| 
Criteria for Evaluation:
 
Safety Variables: AEs, SAEs, clinical signs and symptoms from physical examination, laboratory evaluations, and immunogenicity.
 
Efficacy Variables: Total erythrocyte dAXP from a trough blood sample; trough plasma ADA activity, immune status (B-, T-, and NK-lymphocyte subset analysis, quantitative immunoglobulin concentration [IgA, IgG, IgM]), infections (clinically documented and microbiologically documented), incidence and duration of hospitalizations, growth (height-for-age and weight-for-age Z-scores), and overall survival.
 
Pharmacokinetic Variables: Adagen® and EZN-2279 pharmacokinetics via assessment of plasma ADA activity. The following PK parameters will be computed: Cmax, Ctrough, tmax, AUC(0-t), Kel, and t1/2.
   |                                |   |

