### 5.1. Disease Background

Adenosine deaminase-deficient combined immunodeficiency is a rare, inherited, and often fatal disease. It is characterized by severe and recurrent opportunistic infection, failure to thrive, profound lymphopenia with absent or severely impaired cellular and humoral immune function, and metabolic abnormalities [1,2]. These patients are lymphopenic at birth and predisposed to recurrent illnesses caused by pathogens and opportunistic organisms that often begin within a few weeks. The average age at diagnosis for patients with adenosine deaminase-deficient severe combined immunodeficiency (ADA-SCID) is 4.4 months [3,4].

[figure not shown]
The incidence of ADA deficiency is estimated to be between 1:200,000 and 1:1,000,000 live births [2,4]. ADA deficiency can be categorized into four phenotypes [1]:

- ADA-SCID: The largest number of patients with ADA deficiency (about 85% to 95%) present with ADA-SCID, which is the most severe form of the immunodeficiency.
- Delayed onset ADA deficiency has been identified in 10% to 15% of patients with ADA deficiency which presents after the first year of life and is most likely related to the specific ADA mutation that in such cases results in some residual ADA activity and less profound lymphopenia and immune function.
- Late (or adult) onset ADA deficiency has been identified in a handful of individuals.
- Partial ADA deficiency can be an incidental finding in a healthy individual who has normal immune function and abnormal ADA expression in erythrocytes. Partial ADA deficiency is extremely rare.

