Because Adagen® is administered over extended periods, including life-time administration, and these reactions are reported voluntarily from a small population, it is not always possible to accurately estimate their frequency or establish a definitive causal relationship to drug exposure.

In addition, the assessment of immune system function, which is part of the assessment of efficacy in this clinical study, also represents an important aspect of the assessment of safety.

Refer to the EZN-2279 Investigator's Brochure for additional information.

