#### 12.2.3. Serious Adverse Event

- A *serious adverse event* is an adverse event that in the view of either the investigator or sponsor, results in any of the following outcomes: Results in death
- Is life-threatening (an event that in the view of either the investigator or sponsor, its occurrence places the patient or subject at immediate risk of death; it does not include an event that had it occurred in a more severe form, might have caused death)
- Requires in-patient hospitalization or prolongation of existing hospitalization
- Results in persistent or significant disability/incapacity or substantial disruption of the ability to conduct normal life functions
- Is a congenital anomaly or birth defect
- Is another important medical event that may not be immediately life-threatening or result in death or hospitalization but based upon appropriate medical judgment, may jeopardize the patient or may require medical or surgical intervention to prevent one of the other outcomes listed above. Examples of such events are intensive treatment in an emergency room for

allergic bronchospasm; blood dyscrasias or convulsions that do not result in hospitalization; or development of drug dependency or drug abuse.

The term “severe” is often used to describe the intensity (severity) of an event; the event itself may be of relatively minor medical significance (such as a severe headache). This is not the same as “serious”, which is based on patient/event outcome or action criteria usually associated with events that pose a threat to a patient’s life or functioning.

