7.3 Adverse Events and Other Complications

All adverse events will be coded using the Medical Dictionary for Regulatory Activities (MedDRA) Version 16.0 or the most recent version prior to database lock. Summaries will be presented for all treatment-emergent adverse events (overall and by severity), adverse events determined by the investigator to be treatment-related (overall and by severity), serious adverse events (SAEs), adverse events causing discontinuation from study, adverse events causing discontinuation from study drug, and non-serious adverse events. In addition to being summarized as adverse events, infectious complications and hospitalizations are considered efficacy measures as are summarized in Section 6.3.

The frequency of adverse events will be summarized using descriptive statistics by system organ class (SOC), preferred term and study drug group. Patients are counted only once in each SOC category, and only once in each preferred term category.

Treatment-related adverse event summaries will include adverse events with missing relationship to study drug. For the summaries by severity, patients are counted at the greatest severity. Adverse events missing the flag indicating serious will be excluded from the summary of serious adverse events but included in the summary of non-serious adverse events.

There will be two treatment emergent adverse event summaries provided: all treatment emergent adverse events while the patient takes Adagen[®] study drug and all treatment emergent adverse events while the patient takes EZN-2279, where treatment emergent are new or worsening adverse events that occur while on the respective therapies.

Listings for all adverse events, deaths, serious adverse events, adverse events leading to discontinuation, MedDRA dictionary terms for adverse event descriptions, and adverse event preferred terms by patient number will be presented.

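### Protocol 12.2.1 takes worsening of the disease under study out of the adverse event definition, which conflicts with other protocol sections and, for infections and hospitalizations, with SAP 7.3

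*Protocol*

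**What the plan says.** Protocol 12.2.1 gives a conventional, broad definition of an adverse event and then adds: "Worsening of a medical condition for which the efficacy of the study drug is being evaluated will not be considered an adverse event". The sentence has no qualifier.

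Protocol 12.2.3 builds the serious category on that definition: a serious adverse event "is an adverse event that in the view of either the investigator or sponsor, results in any of the following outcomes". Under Protocol 12.4, SAEs are reported to the sponsor on short deadlines, assessed for expedited reporting, and forwarded to the DSMC.

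Protocol 5.1 describes the disease: "It is characterized by severe and recurrent opportunistic infection, failure to thrive, profound lymphopenia". The synopsis counts lymphocyte subsets and immunoglobulins among the efficacy variables, together with "infections (clinically documented and microbiologically documented), incidence and duration of hospitalizations, growth (height-for-age and weight-for-age Z-scores), and overall survival".

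Other sections point the other way. Protocol 12.3 requires every new event, and every event that becomes more intense or more frequent than at baseline, to be captured. Protocol 10.4.3 makes laboratory abnormalities of clinical importance reportable as AEs. Protocol 5.5 promises special attention to AEs already seen with Adagen, and its lists include infection, pneumonia, failure to thrive and decreased lymphocyte count. It adds that assessing immune function "also represents an important aspect of the assessment of safety". SAP 7.3 says: "In addition to being summarized as adverse events, infectious complications and hospitalizations are considered efficacy measures".

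**The concern.** The features that define ADA-SCID are also efficacy variables in this trial. An investigator who follows 12.2.1 to the letter can class a post-switch infection, a meaningful fall in lymphocytes or failure to thrive as worsening of the condition under evaluation, and record no AE. Because an SAE must first be an AE, the same event would then also miss SAE reporting.

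At stake are the assessments attached to an AE record: severity, causality, seriousness and, for SAEs, the expedited-reporting decision and transmission to the DSMC. Protocol 5.3.2 states that EZN-2279 has had no earlier clinical study, and patients are moving to it from an established product. Weaker disease control after the switch is a foreseeable harm that the safety data should show in a consistent way. With the sections in conflict, two sites could code the same event differently and each cite the protocol.

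**Working it through.** No figure in the plan depends on this sentence, so there is nothing to recompute. The check sets the sections side by side.

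1. **Does the exclusion reach these events?** Protocol 12.2.1 excludes worsening of the condition whose efficacy is under evaluation. Protocol 5.1 characterizes that condition by infection, failure to thrive and lymphopenia, and the synopsis makes infection, growth and lymphocyte subsets efficacy variables. A literal reading therefore reaches them. It is not the only possible reading, since a discrete infection can also be seen as a new event.

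2. **Does it carry through to SAEs?** Yes. Protocol 12.2.3 defines an SAE as a kind of AE. Protocol 10.4.1 and 10.4.2 also make recording of examination and vital-sign findings depend on the AE definition.

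3. **Which text conflicts, and which routes do not depend on the AE label?**

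| Event after the switch | Text that points to recording an AE | Route independent of the AE label |
|---|---|---|
| Infection | Protocol 12.3 and 5.5; SAP 7.3 | Classified and recorded as clinical status (Protocol 10.5.3.1) |
| Event leading to hospitalization | Protocol 12.3; SAP 7.3 | All hospitalizations go to sponsor drug safety (Protocol 10.5.3.2) |
| Meaningful lymphocyte decrease | Protocol 10.4.3, 12.3 and 5.5 | Immune status summaries (SAP 6.3.3) |
| Failure to thrive | Protocol 12.3 and 5.5 | Growth summaries (SAP 6.3.4) |
| Death | Protocol 12.3 and 12.2.3 | All deaths go to sponsor drug safety at once (Protocol 10.5.3.4) |

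4. **Can the analysis repair under-recording?** No. SAP 7.3 tabulates treatment-emergent AEs, "where treatment emergent are new or worsening adverse events that occur while on the respective therapies", with no exclusion for the disease under study, but it can count only what sites entered as AEs. The efficacy side does not replace those tables. SAP 6 presents efficacy summaries for EZN-2279 only, and SAP 6.3.4 specifies infection and hospitalization totals for the EZN-2279 treatment period. The AE tables by study drug are the specified summaries that also cover the lead-in and run through maintenance.

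5. **What do the independent routes leave open?** Protocol 10.5.3.2 sends hospitalizations to drug safety but states no deadline and no causality assessment. A serious infection managed without admission could qualify under the medical-judgement criterion in 12.2.3. If it is not recorded as an AE and is not fatal, no equivalent route exists.

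**The case against.** The strongest reply is that the protocol as a whole already directs sites to record these events. Section 12.3 says all new or worsening events are captured, 10.4.3 covers laboratory changes expressly, and SAP 7.3 shows that the sponsor counts infections as AEs. On this view the sentence in 12.2.1 concerns only general progression of the disease. That reading is reasonable and may be the intended one. It still leaves an unqualified sentence, in the section that defines an AE, that permits the opposite. The conflict is not resolved on the page.

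A reader might infer three stronger things that the documents do not support.

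- **That the signal of lost disease control disappears.** It does not. Trough dAXP is the primary endpoint. ADA activity, immune status, infections, hospitalizations and growth are all collected, and all efficacy data are listed (SAP 6). The DSMC reviews safety, ADA activity and dAXP at set times (Protocol 7.7).
- **That AE counts on Adagen and EZN-2279 cannot be compared because of this sentence.** One definition applies from the first lead-in dose (Protocol 12.1), and no difference in its use between the two drugs is shown.
- **That every listed event contradicts the SAP.** SAP 7.3 names only infectious complications and hospitalizations. For lymphocyte decreases the direct conflict is with Protocol 10.4.3. For failure to thrive it is with 5.5 and 12.3.

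**Conclusion.** The point holds as a conflict between stated rules. Protocol 12.2.1 allows events that Protocol 12.3, 10.4.3 and 5.5 treat as reportable to be left out of the AE and SAE records, and SAP 7.3 assumes that infections and hospitalizations are there. The consequence is possible incomplete or uneven classification, with severity, causality and expedited-reporting assessment missing for some events. It is not loss of detection.

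The documents do not support a numerical size. A reader might take one omitted patient in six, 1/6 = 16.7 percentage points, as the effect on SAE incidence. That assumes a denominator of six. Safety uses the as-treated population, which includes patients given only lead-in Adagen (SAP 4.1), and more than six may be enrolled (Protocol 9.1). A patient who has another recorded SAE would also still be counted.

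The conclusion assumes that at least some sites read 12.2.1 literally. The documents supplied contain no further instruction to sites that would settle the reading.

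**What to change.** Delete the sentence in Protocol 12.2.1, or replace it with wording such as: *Infections, events leading to hospitalization, clinically meaningful laboratory abnormalities (including lymphocyte decreases) and failure to thrive that are new or worsen after the first lead-in dose are recorded as AEs, and as SAEs when a criterion in 12.2.3 is met, even though they are also efficacy measures.*

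The wording names the event leading to hospitalization because 12.2.3 treats hospitalization as a seriousness criterion and 12.3 asks for a diagnosis. It brings 12.2.1 into line with Protocol 12.3, 10.4.3 and 5.5 and, for infections and hospitalizations, with SAP 7.3. The SAP text needs no change.

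The cost is one sentence in an amendment, site retraining and slightly higher AE counts. Infection and hospitalization records already collected should be checked once against the AE data, so that events left out under the present sentence are found and classified.

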#### 12.2.2. Unexpected Adverse Event

An unexpected adverse event is one that is not listed in the Investigator Brochure or is not listed at the specificity or severity that has been observed.

For example, under this definition, hepatic necrosis would be unexpected (by virtue of greater severity) if the investigator brochure referred only to elevated hepatic enzymes or hepatitis. Similarly, cerebral thromboembolism and cerebral vasculitis would be unexpected (by virtue of greater specificity) if the investigator brochure listed only cerebral vascular accidents. “Unexpected,” as used in this definition, also refers to adverse events or suspected adverse reactions that are mentioned in the investigator brochure as occurring with a class of drugs or as anticipated from the pharmacological properties of the drug, but are not specifically mentioned as occurring with the particular drug under investigation.

#### 12.2.3. Serious Adverse Event

- A *serious adverse event* is an adverse event that in the view of either the investigator or sponsor, results in any of the following outcomes: Results in death
- Is life-threatening (an event that in the view of either the investigator or sponsor, its occurrence places the patient or subject at immediate risk of death; it does not include an event that had it occurred in a more severe form, might have caused death)
- Requires in-patient hospitalization or prolongation of existing hospitalization
- Results in persistent or significant disability/incapacity or substantial disruption of the ability to conduct normal life functions
- Is a congenital anomaly or birth defect
- Is another important medical event that may not be immediately life-threatening or result in death or hospitalization but based upon appropriate medical judgment, may jeopardize the patient or may require medical or surgical intervention to prevent one of the other outcomes listed above. Examples of such events are intensive treatment in an emergency room for

allergic bronchospasm; blood dyscrasias or convulsions that do not result in hospitalization; or development of drug dependency or drug abuse.

The term “severe” is often used to describe the intensity (severity) of an event; the event itself may be of relatively minor medical significance (such as a severe headache). This is not the same as “serious”, which is based on patient/event outcome or action criteria usually associated with events that pose a threat to a patient’s life or functioning.

#### 12.2.4. Relationship to Study Drug

The Investigator must attempt to determine if an adverse event is in some way related to the use of the study drug. This relationship should be described based upon the following definitions:

- **Unrelated:** The adverse event is clearly due to causes distinct from the use of the study drug, such as a documented pre-existing condition, the patient’s clinical state, environmental factors, the effect of other concomitant medications or treatments administered.
- **Unlikely:** The adverse event does not follow a reasonable temporal sequence from administration of the study drug, does not follow a known response pattern to the study drug, and could readily have been due to other causes such as the patient’s clinical state, environmental factors, the effect of other concomitant medications or treatments administered.
- **Possible:** The adverse event follows a reasonable temporal sequence from administration of the study drug and follows a known response pattern to the study drug, *BUT*, the adverse event could readily have been produced by the patient’s clinical state, environmental factors, the effect of other concomitant medications or treatments administered.
- **Probable:** The adverse event follows a reasonable temporal sequence from administration of the study drug and follows a known response pattern to the study drug, *AND* cannot be reasonably explained the patient’s clinical state, environmental factors, the effect of other concomitant medications or treatments administered. The event improves upon discontinuation of the study drug.
- **Definite:** The adverse event follows a reasonable temporal sequence from administration of the study drug and follows a known response pattern to the study drug. Based on the known pharmacology of the study drug, the event is clearly related to the effect of the study drug. The adverse event improves upon discontinuation of the study drug and reappears upon repeat exposure.

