#### 5.3.2. Clinical Studies

No clinical studies of EZN-2279 have been performed.

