## 5.5. Potential Risks and Benefits

EZN-2279 has been developed to be similar to Adagen®. [REDACTED]

[REDACTED] The more stable linker for EZN-2279 imparts the potential for reduced immunogenicity due to improved shielding of the rADA and subsequently may decrease the incidence of neutralizing antibodies, and in animal models imparts a longer half-life compared to Adagen®. The enzyme used for manufacturing EZN-2279 is recombinant, and based on the same bovine sequence as Adagen®. [REDACTED]

In addition to monitoring adverse events/experiences (AEs) as required in all clinical trials, particular attention will be paid to AEs that have been observed with Adagen®. It is possible that EZN-2279 will have side effects and DLTs similar to those of Adagen® [40].

Clinical trial experience with Adagen® is based on the patient population for this orphan drug, estimated to be approximately 100 patients worldwide [Leadiant Biosciences data on file]. Based on six

patients, the following adverse reactions are reported in the Adagen® product label: pain at the injection site (two patients) and headache (one patient) [40].

In addition, during post-approval use of Adagen®, the following adverse reactions have been identified, regardless of relationship with the drug or the disease [40, Leadiant Biosciences data on file]:

- At least 5% of cases: Respiratory failure, failure to thrive, drug level decreased, respiratory tract infection, thrombocytopenia, adverse reactions pertaining to an immune reaction (such as hemolytic anemia and neutralizing antibodies), infection, pneumonia, and death due to an unknown cause
- 3% to 4% of cases: Autoimmune hemolytic anemia, drug-specific antibody present, injection-site erythema, urticaria, adenovirus infection, bovine tuberculosis, brain abscess, convulsion, developmental delay, drug ineffective, diarrhea, encephalitis, Epstein-Barr virus infection, erythema, hearing impairment, hepatoblastoma, Hodgkin's disease, interstitial lung disease, lung disorder, lymphocyte count decreased, nervous system disorder, sepsis, thrombocytopenia, and viral pneumonia

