#### 12.4. Reporting Serious Adverse Events

All serious adverse events (SAEs), regardless of relationship to study drug, must be reported to Leadiant Biosciences as described below.

- Serious adverse events that are fatal or life-threatening must be reported to Leadiant Biosciences or their designee by telephone *immediately* after site personnel first become aware of the event. Within 24 hours, the Leadiant Biosciences Serious Adverse Event Form must be faxed to the medical monitor or designee regardless of whether full information regarding the event is known or not. If full information is not known, additional follow-up by the Investigator will be required.
- All other serious adverse events must be reported to the Leadiant Biosciences medical monitor or designee within 24 hours by phone, e-mail or fax after becoming aware of the event. Within 48 hours, the Leadiant Biosciences Serious Adverse Event Form must be faxed to the medical monitor or designee regardless of whether full information regarding the event is known or not. If full information is not known, additional follow-up by the Investigator will be required.

Report all SAEs to the Leadiant Biosciences safety representative listed in the Study Reference Manual.

All SAEs will be evaluated by the Leadiant Biosciences Medical Monitor or designee. If meeting the requirements for expedited reporting (i.e., serious, unexpected and related), Leadiant Biosciences will so report the adverse event to all regulatory authorities with jurisdiction over ongoing trials with the study drug and to all other investigators involved in clinical trials with EZN-2279.

The Investigator must report all SAEs reported by Leadiant Biosciences to regulatory authorities in an expedited manner to the reviewing IRB. For all other SAEs, the Investigator must report all serious adverse events in accordance with the requirements of the reviewing IRB.

Leadiant Biosciences will forward all reports of SAEs to the DSMC and the Lead PI.

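### The causality scale has no valid grade for a well-timed reaction that is new to EZN-2279, so such an event may be rated Unlikely and be missed as related

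*Protocol*

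**What the plan says.** Protocol 12.2.4 asks the investigator to grade each adverse event on a five-level scale. Possible, Probable and Definite share the same opening condition: the event "follows a reasonable temporal sequence from administration of the study drug and follows a known response pattern to the study drug". An Unlikely event has implausible timing, "does not follow a known response pattern to the study drug, and could readily have been due to other causes". For Unrelated, "The adverse event is clearly due to causes distinct from the use of the study drug".

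Protocol 5.3.2 states: "No clinical studies of EZN-2279 have been performed". The nearest source of a known pattern is Adagen; Protocol 5.5 says "It is possible that EZN-2279 will have side effects and DLTs similar to those of Adagen".

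Two later steps use the causality judgement:

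- SAP 7.3 plans summaries of "adverse events determined by the investigator to be treatment-related (overall and by severity"). It does not say which of the five grades count as treatment-related. SAP 7.3 and 10.6 both treat a missing relationship as related.
- Protocol 12.4 sets the expedited rule: "If meeting the requirements for expedited reporting (i.e., serious, unexpected and related), Leadiant Biosciences will so report the adverse event". Protocol 12.2.2 begins its definition of the second condition with "An unexpected adverse event is one that is not listed in the Investigator Brochure" and then widens it to events listed with less specificity or severity, or mentioned only for the class or the pharmacology.

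**The concern.** A known pattern is reasonable supporting evidence for causality in a drug with a long record. Here it is a condition of entry to every related grade, in a product with no human record. EZN-2279 differs from Adagen in its recombinant enzyme and its more stable linker, so a reaction not seen before is one of the things first human exposure should reveal. The scale has no place for such a reaction, however convincing the timing.

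What is at stake is the reading of the safety data. If the investigator settles on Unlikely because every related grade is barred, the treatment-related table may understate what the drug did. A serious new reaction may also be judged not related when expedited reporting is considered. In a trial planned around six evaluable patients, one such event matters.

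**Working it through.** The plan gives no figure to reproduce here, and no rate or sample-size formula applies. The check is whether the five definitions cover the case.

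**Inputs.** The five definitions (Protocol 12.2.4); no previous clinical study (Protocol 5.3.2); the requirement to record relationship for each event by reference to these definitions (Protocol 10.4.4 and 12.3).

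**Step 1: the test case.** Take an event with reasonable timing, no known response pattern, and no cause to which it is clearly due other than the drug.

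| Grade | Conditions, all required | Result |
|---|---|---|
| Unrelated | Clear other cause | Not met |
| Unlikely | Implausible timing; no known pattern; other causes readily possible | Fails on timing |
| Possible | Reasonable timing; known pattern; other causes readily possible | Fails on pattern |
| Probable | Reasonable timing; known pattern; no other reasonable explanation; improves on stopping | Fails on pattern |
| Definite | Reasonable timing; known pattern; clear from known pharmacology; improves on stopping; recurs on re-exposure | Fails on pattern |

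**Step 2: vary the other features.** Another cause is either readily possible or not a reasonable explanation (2 levels). The course is no improvement on stopping, improvement without recurrence, or improvement with recurrence (3 levels). That gives 2 × 3 = 6 profiles.

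- Gradable as Possible, Probable or Definite: 0 of 6.
- Fitting no grade at all: 6 of 6. This includes the profile with no other explanation, improvement on stopping and recurrence on re-exposure.

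These six are logical combinations, not patients or frequencies.

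**Step 3: test the repair.** Remove the pattern condition from Possible and Probable only.

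- Another cause readily possible: all 3 profiles become Possible.
- No other reasonable explanation: the 2 that improve on stopping become Probable.
- Total: 3 + 2 = 5 of 6. The sixth (no other explanation, no improvement on stopping) still has no grade, because Probable needs improvement and Possible needs an alternative cause.

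Add a rule that plausible timing without a clearly distinct cause is at least Possible. The sixth profile is then covered: 5 + 1 = 6 of 6.

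**Step 4: follow the event downstream.**

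- *Treatment-related table.* If the field is blank, the SAP counts the event as related. If Unlikely is entered, the missing-data rule does not apply, and the outcome depends on a mapping from grades to treatment-related that the SAP does not give.
- *Expedited reporting.* The event must be serious, unexpected and related. A reaction never described before meets the unexpected condition easily, but the pattern condition bars every related grade on the only causality scale the protocol defines. Protocol 12.4 does not say whether that scale or the sponsor's own judgement decides.

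**The case against.** The strongest reply is that nothing forces the loss. A reader might infer that a new reaction is bound to drop out of the treatment-related table. The documents do not support that: no section sends an ungradable event to Unlikely, a missing relationship is counted as related, and the SAP never says that Unlikely means not related. This stands as a limit on the claim. It does not remove the gap, because relationship is to be recorded for each event using these definitions, and a completed form never triggers the missing-data rule.

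A reader might also infer that a serious new reaction could not qualify for expedited reporting, or that unexpected and related nearly exclude each other. That goes too far. All serious events go to the sponsor whatever their causality, its medical monitor or designee evaluates each one, and the reports go to the monitoring committee. Protocol 12.4 does not tie the word related to the investigator's grade. Protocol 12.2.2 also makes an event unexpected by severity, by specificity, or when it is known only from the class or pharmacology; such an event can follow a known pattern and meet both conditions.

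The affected set is also limited. Adagen experience supplies some known patterns, and Protocol 13.2.2 uses study drug to cover both products. Signs of allergy have their own 48-hour report, serious or not (Protocol 12.4.1), although that report does not settle relatedness. Finally, treatment-emergent and serious events are tabulated whatever their causality, all events are listed, and the monitoring committee reviews safety at four points (Protocol 7.7). With so few patients, each event can be read individually. These safeguards keep the event visible; they do not give it a correct causality grade.

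**Conclusion.** The concern holds as a gap in a stated rule, with possible rather than certain consequences. On the literal text, all three related grades exclude a well-timed reaction new to both Adagen and EZN-2279, and neither remaining grade fits it. The event may then be lost from the treatment-related table and may be judged not related under the expedited rule.

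The size cannot be put as a rate. A reader might infer a contrast of 0/6 against 1/6 patients (1/6 = 16.7%). That assumes one such event, an Unlikely rating, a mapping of Unlikely to not related, and a denominator of six. Six is the number of evaluable patients; safety uses the as-treated population, which also keeps non-completers, who are to be replaced (Protocol 9.5.3 and 13.2.2; SAP 4.1).

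The conclusion rests on two assumptions: that investigators apply the definitions as written, with every listed condition required, and that the reaction is not already known from Adagen or the animal studies.

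**What to change.** - **Protocol 12.2.4:** make the known response pattern supportive rather than required for Possible and Probable. State that an event with plausible timing and no clearly distinct cause is at least Possible, even if never described before. Both changes are needed, because the first alone leaves one profile in six without a grade.
- **SAP 7.3:** define treatment-related as Possible, Probable, Definite or missing.
- **Protocol 12.4:** state whether the investigator's or the sponsor's causality judgement drives expedited reporting.

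The cost is a few sentences in the protocol and one in the SAP. The downside is that a few more events will be classed as related.
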